Annex 1. Exjade SmPC 125 mg, 250mg, 500 mg	
Annex 2. Child Health Questionnaire (CHQ-PF28)	

Abbreviations and Definition of Terms

CONFIDENTIAL

DEEP Consortium

DEEP2-Efficacy/Safety Study Protocol

Protocol No. DEEP-2

AE	Adverse Event
ANC	Absolute Neutrophil Count
AR	Adverse Reaction
CHQ	Child Health Questionnaire
CRF	Case Report Form
DFO	Deferoxamine
DFP	Deferiprone
DFX	Deferasirox
dL	decilitre
DSMC	Data Safety Monitoring Committee
dw	dry weight
EC	Ethics Committee
ECG	Electrocardiogram
EMA	European Medicines Agency
EU	European Union
Fe	Iron
GCP	Good Clinical Practice
GEE	Generalised Estimating Equations
GI	gastrointestinal
Hb	Haemoglobin
HRQoL	Health Related Quality of Life
IEC	Independent Ethics Committee
IMP	Investigational Medicinal Product
IRB	Institutional Review Board
ITT	Intent To treat
L	litre
LIC	Liver Iron Concentration
MAH	Marketing Authorization Holder
mg	milligram
ms	milliseconds
PDCO	Paediatric Committee
PIP	Paediatric Investigational Plan
PK	Pharmacokinetic
PP	Per Protocol
QoL	Quality of Life
QPPV	Qualified Person for Pharmacovigilance
REB	Research Ethics Board
SAE	Serious Adverse Event
SAR	Serious Adverse Reaction
SC	Safety Contact
SCD	Sickle Cell Disease
SID	Study Identification Number
SmPC	Summary of Product Characteristics
SPM	Study Procedures Manual
UAR	Unexpected Adverse Reaction
WBC	White Blood Cells
WHO	World Health Organization

1. PROTOCOL NUMBER

This study is being conducted under protocol number: **DEEP-2**

EudraCT number: **2012-000353-31**

2. OBJECTIVES

2.1Primary Objective

The primary objective of this study is to assess the non-inferiority of deferiprone (DFP) compared to deferasirox (DFX) in terms of changes of ferritin levels and heart iron concentration in paediatric patients affected by hereditary haemoglobinopathies requiring chronic transfusions and chelation.

2.2Secondary objectives

Secondary objectives of this study are:

- to assess treatment efficacy in terms of ferritin levels
- to assess treatment efficacy in terms of cardiac MRI T2* in patients over 10 years of age able to perform MRI scan without sedation
- to estimate the efficacy of treatments in terms of liver iron concentration (LIC) measured by MRI in all paediatric subjects able to have MRI scan without sedation
- to evaluate the safety and tolerability profile of treatments
- to assess healthcare resources utilisation and patient global assessment, including compliance and quality of life (QoL) evaluation
- to confirm the influence of demographic covariates on the pharmacokinetic disposition of treatments across the study population.

2.3Exploratory objectives

Additional and exploratory objectives of the study include the assessment of the correlation between systemic exposure to the investigational drugs and serum ferritin levels observed after one year treatment.

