4.4.5 Pharmacokinetics

Plasma samples will be collected at the end of treatment for the assessment of drug concentrations at steady-state conditions in all the patients until a patients' number leading to statistically significant analysis is reached. Pharmacokinetic data will then be analysed to confirm the influence of relevant covariates (e.g., demographics) on the systemic exposure to drug treatments.

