6.3 Dose Adjustments

Dose adjustments for both DFP and DFX will be allowed for efficacy reasons (scaling up) or for safety reasons including the presence of markers indicative of over-chelation (scaling down).

DFP can be scaled up in steps of 12.5 mg/kg/day (to a maximum daily dose of 100 mg/kg) according to the individual patient's response defined as an increase of serum ferritin levels > 20% compared to the previous determination.

DFX will be scaled up in steps of 5 to 10 mg/kg (to a maximum daily dose of 40 mg/kg) according to the individual patient's response defined as an increase of ferritin levels > 20% compared to the previous determination.

For patients with a stable serum ferritin value >1500 (no increase or any increase <20%) and not showing a downtrend over a 3-month-period , DFP or DFX can be also increased.

DFP and DFX must be scaled down for the safety reasons detailed in **Table 4**.

Table 4. Scale down adjustment for DFP and DFX (safety reasons)

Serum creatinine increased by >33% from baseline OR Reduction in creatinine clearance (estimated with the Schwartz formula) ≤ 90ml/min and >60 ml/min in two consecutive measurements	No dose adjustment.	Reduce DFX in steps of 10 mg/kg/day until value returns to baseline value and continue DFX with the adjusted dose for 1 month. If the increase persists interrupt DFX. If after DFX interruption value returns to baseline value or > 90 ml/min for creatinine clearance restart DFX at 50% of the last dose and then escalate by 10 mg/kg/day at 1 month intervals provided that value increase does not recur. Monitor serum creatinine, creatinine clearance and urine protein/creatinine ratio weekly (+/- 7 days) during the period of abnormal value and during the first month after dose modification, then monthly.
Urine protein/creatinine ratio ≥ 0.5 in two consecutive measurements	No dose adjustment.	Reduce DFX in steps of 10 mg/kg/day until value returns to < 0.5. If the increase persists interrupt DFX. After the ratio improves, restart DFX at 50% of the last dose and then escalate by 10 mg/kg/day at 1 month intervals provided that value increase does not recur. Monitor serum creatinine, creatinine clearance and urine protein/creatinine ratio weekly (+/- 7 days) during the period of abnormal value and during the first month after dose modification, then monthly.

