ALT or AST > 10 ULN	Interrupt DFP. When levels return to < 5 ULN, restart DFP at 50% of the last dose and after 1 month scale it back up to the former dose.	Interrupt DFX. When levels return to < 5 ULN, restart DFX at 50% of the last dose and then escalate by 10 mg/kg/day at 1 month intervals provided that value increase does not recur.

CONFIDENTIAL

Severe skin rash	No dose adjustment.	Interrupt DFX . Once resolved, restart DFX at 50% of the last dose and then escalate by 5 mg/kg/day at two-weeks intervals.
Ferritin \leq 500 ng/ml	Reduce DFP to 50% of last dose. If ferritin is still <500 ng/ml at subsequent monthly evaluation, DFP may continue having consulted the Coordinating Investigator. When value returns > 500 ng/ml DFP can be scaled up to full dose.	Reduce DFX to 50% of last dose. If ferritin is still <500 ng/ml at subsequent monthly evaluation, DFX may continue having consulted the Coordinating Investigator. When value returns > 500 ng/ml restart DFX at 50% of the last dose and then escalate by 10 mg/kg/day at 1 month intervals.
Neutropenia(neutrophil count $<1500/\text{mm}^3$ and $\geq 1000/\text{mm}^3$ in two consecutive measurements)*	Interrupt DFP and monitor neutrophil count every 1-3 days or more frequently. When value returns $> 1500/\text{mm}^3$ for two consecutive measurements, and if deemed safe by the investigator, restart DFP at the last dose after having consulted the Coordinating Investigator.	Interrupt DFX and monitor neutrophil count every 1-3 days or more frequently. When value returns $> 1500/\text{mm}^3$ for two consecutive measurements, and if deemed safe by the investigator, restart DFX at the last dose after having consulted the Coordinating Investigator.
Moderate Neutropenia (neutrophil count $<1000/\text{mm}^3$ and $> 500/\text{mm}^3$) OR Severe Neutropenia/Agranulocytosis (neutrophil count $< 500/\text{mm}^3$) Infection	Interrupt DFP. Exit from the protocol.	Interrupt DFX. Exit from the protocol.

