7.3.7 Pharmacokinetics

Pharmacokinetic assessment will be performed in patients who complete the study. Last dose of the study treatments (DFP and DFX) must be administered in the clinic under supervision of qualified staff at the beginning of the visit V15 and time of administration must be recorded accordingly and reported in the CRF. A sample (2 mL) for the assessment of peak drug concentrations should be collected within 4 hours after dosing according to the sparse sampling scheme specified in the SPM.

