The correlation between DFP and DFX disposition and serum ferritin levels after 1 year treatment will be tested as exploratory objective of the trial.

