11.2 Study population

Intent to treat population

For the intent to treat (ITT) analysis all patients that have been randomized and start therapy will be included.

Per protocol population

Patients in the per protocol (PP) population for the primary efficacy analysis (PP1) are those that have received the study drugs and for whom the composite endpoint is available at baseline and after 1 year treatment, without major protocol violations.

For the secondary efficacy evaluation assessed as non-inferiority of DFP to DFX in terms of serum ferritin levels the PP population (PP2) includes only patients for whom the measure of serum ferritin is available at baseline and after 1 year treatment.

For the secondary efficacy evaluation assessed as non-inferiority of DPF to DFX in terms of successfully chelated patients according to cardiac MRI T2* the PP population (PP3) includes only patients for whom the measure cardiac MRI T2* is available at baseline and after 1 year treatment.

Safety population

The population for the safety and tolerability analysis will include all patients having received at least one dose of study medication.

PK and PKPD population

The population for the pharmacokinetic and subsequent exploratory analyses (e.g. correlation between systemic exposure and ferritin levels) will include patients who have received the investigational drugs throughout the duration of the study (i.e., 1 year) and have had a blood sample collected for the assessment of drug concentrations in plasma.

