11.9 Exploratory PKPD analysis

The main objective of this analysis is to explore whether a correlation can be established between treatment response and steady-state concentrations of the investigational drugs. Therefore, pharmacokinetic data collected for DFP and DFX will be analysed in conjunction with the primary pharmacodynamic endpoints (ferritin and MRI). Data will subsequently be modelled using nonlinear mixed effects modelling, as implemented in the software NONMEM ([name], USA).

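### The exploratory exposure-response analysis relates end-of-study drug exposure to one-year ferritin although dose is steered by ferritin, so a direct correlation is biased toward the wrong sign

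*Combined protocol and SAP*

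**What the plan says.** Three places describe the same exploratory analysis in different terms.

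- Section 2.3 names the "correlation between systemic exposure to the investigational drugs and serum ferritin levels observed after one year treatment".
- Section 11.1 says: "The correlation between DFP and DFX disposition and serum ferritin levels after 1 year treatment will be tested as exploratory objective of the trial".
- Section 11.9 aims to "explore whether a correlation can be established between treatment response and steady-state concentrations of the investigational drugs". It brings in ferritin and MRI as the pharmacodynamic measures and names nonlinear mixed-effects modelling. It does not mention dose history, exposure that varies over time, baseline ferritin or ferritin-guided dosing.

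Exposure is measured once. Section 4.4.5 says "Plasma samples will be collected at the end of treatment for the assessment of drug concentrations at steady-state conditions", and Section 7.3.7 adds "A sample (2 mL) for the assessment of peak drug concentrations should be collected within 4 hours after dosing", in patients who complete the study. Under Section 11.2 the PK and PKPD population "will include patients who have received the investigational drugs throughout the duration of the study (i.e., 1 year").

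Dose depends on ferritin in both arms (Section 6.3). It can go up "according to the individual patient's response defined as an increase of serum ferritin levels > 20% compared to the previous determination", and also when ferritin is stable above 1500 with no downward trend over three months. At 500 ng/mL or below, Table 4 says for DFP: "Reduce DFP to 50% of last dose. If ferritin is still <500 ng/ml at subsequent monthly evaluation". The DFX column has the same halving. Section 6.2 also allows a DFX start of 30 mg/kg when ferritin exceeds 2500 ng/mL or T2* is below 20 ms.

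**The concern.** An exposure-response analysis is informative when exposure varies for reasons unrelated to the outcome. Here part of the variation in V15 exposure is produced by the outcome. Patients whose ferritin stays high or rises move toward the top of the dose range, and patients whose ferritin falls low are put on half dose. This is confounding by indication, built in by the dosing rules.

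The V15 sample also reflects the dose at the end of the year, not the doses that produced the 12-month change. In addition, patients withdrawn under Section 9 for a large quarterly ferritin rise, or for an adverse event requiring a change of chelation, are outside the PKPD set.

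At stake is the reading of one named exploratory objective. A report that higher exposure goes with higher ferritin could describe how doses were assigned and say nothing about what the drug does.

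**Working it through.** **No plan figure to reproduce.** The documents give no expected correlation, sample size or power for this analysis. The simulations use 155 patients per arm, from the 310 evaluable patients in Section 11.12 (310 / 2 = 155).

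**Where the bias comes from.** If concentration is proportional to dose divided by clearance, then log C = log dose - log CL, and

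Cov(log C, log F12) = Cov(log dose, log F12) - Cov(log CL, log F12),

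where dose and C are the V15 values and F12 is ferritin at month 12. The ferritin rules make the first term positive. A beneficial drug effect makes the second part negative, because slow clearance gives more exposure and lower ferritin. The sign of the sum depends on which part is larger. With fixed dosing the first term is zero. If C is divided by dose, only -log CL remains and the first term drops out.

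**Main simulation.** 300 trials per scenario, monthly ferritin, the ferritin rules of Sections 6.2 and 6.3 and the ferritin withdrawal rule of Section 9. The drug truly lowers ferritin throughout. Assumed, because the documents do not give them:

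- median baseline ferritin 1200, 1800 or 2500 ng/mL, log-SD 0.6
- between-patient log-SD of clearance 0.2, 0.3 or 0.5
- two drug-effect sizes (full and half)
- SD of yearly log-ferritin drift 0.25
- assay noise 0.12, concentration noise 0.3
- half of the optional increases taken, DFX step 7.5 mg/kg

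Mean Spearman correlation of V15 concentration with month-12 ferritin among completers, full effect:

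| Arm | Median ferritin | CL log-SD 0.2 | 0.3 | 0.5 |
|---|---|---|---|---|
| DFP | 1200 | +0.20 | +0.14 | -0.01 |
| DFP | 1800 | +0.08 | 0.00 | -0.14 |
| DFP | 2500 | +0.02 | -0.05 | -0.19 |
| DFX | 1200 | +0.29 | +0.21 | +0.06 |
| DFX | 1800 | +0.20 | +0.11 | -0.06 |
| DFX | 2500 | +0.12 | +0.04 | -0.15 |

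- Fixed dosing, for comparison: -0.09 to -0.12, with a positive sign in 8 to 16% of trials.
- Both effect sizes together: DFP -0.19 to +0.20, DFX -0.15 to +0.29. The mean is positive in 25 of 36 scenarios (10 of 18 DFP, 15 of 18 DFX).
- Central case (median 1800, clearance log-SD 0.3, full effect): the sign is positive in 51% of DFP trials and 92% of DFX trials.
- The correlation of V15 dose with month-12 ferritin, the first term above, is +0.26 to +0.61 in every titrated scenario.

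**Other sets of assumptions.** Set A fixes median ferritin at 1800 and clearance variability at 30%, and lists no concentration noise. Set B varies median ferritin from 1200 to 2500 and clearance log-SD from 0.2 to 0.5, with concentration noise 0.3. A further run is shown as a third line.

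| Run | No effect, DFP | No effect, DFX | True benefit, DFP | True benefit, DFX |
|---|---|---|---|---|
| A | +0.23 to +0.33 | +0.42 to +0.55 | +0.05 to +0.19 | +0.25 to +0.43 |
| B | +0.11 to +0.39 | +0.27 to +0.54 | -0.08 to +0.33 | +0.03 to +0.47 |
| Further | +0.09 to +0.31 | +0.20 to +0.44 | -0.22 to +0.20 | -0.17 to +0.32 |

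**What removes the bias.**

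- V15 concentration against *change* from baseline: -0.47 to +0.03 in the main simulation. The sign is mostly right, but the relation is weakened.
- Dose-normalised exposure against change from baseline: about 0 with no effect (sets A and B). With a true benefit it is -0.27 to -0.48 (A) and -0.10 to -0.42 (B). A significant wrong sign occurs in 4% of trials or fewer.
- Individual 1/clearance against change, main simulation: -0.13 to -0.60. This uses true clearance, so an estimate from one sample would do less well.
- Cumulative exposure from dose history against change: -0.02 to -0.59. The sign is right, but close to zero at the weak end, because dose history also responds to ferritin.

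**The case against.** The strongest reply is that a raw rank correlation is not what Section 11.9 describes. It speaks of treatment response, and the success criteria in Section 4.3.1 are defined against baseline. It names mixed-effects modelling, and Section 11.8 adds DEEP-1 data and covariate modelling, a framework that normally yields individual clearance. Section 11.1 says disposition, not concentration. Moving to change from baseline alone nearly removes the reversal.

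This stands in part: a suitable model is possible within what is named. But Sections 2.3 and 11.1 put ferritin after one year as the outcome. The covariates in Section 11.8 act on pharmacokinetic parameters, not on the exposure-ferritin relation. Naming a model class does not remove confounding by the dosing rules when dose history and baseline ferritin are left out.

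A reader might infer more than the documents support:

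- *That the sign will reverse, almost surely for DFX.* Set A gave a significant wrong sign in 40% (DFP) and 97% (DFX) of runs despite a true benefit. Those rates rest on fixed values of baseline ferritin and clearance variability that the documents do not give. The main simulation shows the correct sign in part of its grid.
- *That the PKPD set drops patients whom the primary analysis counts as failures.* The primary analysis is on PP1, and Section 11.6 assigns failure for a non-estimable endpoint in the ITT analysis. Sections 9 and 11.13 state a general failure rule, so the contrast is not clear-cut.
- *That a comparison of exposure-response between arms would mislead.* None is planned.
- *That paediatric dosing will follow from this result.* No section says so. Dosing under 6 years comes from DEEP-1.

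**Conclusion.** The concern holds as a bias toward a positive sign in a direct correlation of V15 exposure with one-year ferritin. Across all runs the correlation is +0.09 to +0.39 (DFP) and +0.20 to +0.55 (DFX) when exposure has no effect. With a true benefit it is -0.22 to +0.33 (DFP) and -0.17 to +0.47 (DFX). Reversal is possible, not certain. It is most likely when clearance varies little and ferritin is lower, and fades when clearance varies widely and ferritin is high.

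The direction follows from the dosing rules. The size rests on assumed clearance variability, baseline ferritin, noise and uptake of optional increases. The objective is exploratory and the non-inferiority conclusion is unaffected, so this is a worthwhile improvement to the plan and not a defect in the main result.

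**What to change.** Amend Sections 2.3, 11.1 and 11.9; no dosing rule changes.

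1. Use one exposure term throughout, in place of systemic exposure, disposition and steady-state concentrations, and define it.
2. Specify one of two analyses. (a) Relate change in ferritin from baseline to dose-normalised exposure, through individual clearance from the Section 11.8 model. (b) Model the serial ferritin values on exposure built from the recorded dose history, with baseline ferritin included. Option (a) is simpler. Option (b) needs the full time course, since a plain correlation with cumulative exposure remains weakened.
3. State that the raw V15 concentration-ferritin correlation is descriptive and not causal, and that results apply to completers only.

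The data already exist: dispensing records (Section 6.1), compliance at each visit (7.3.26), and monthly local and quarterly central ferritin (7.3.12). No new samples or visits are needed, and clearance need not be imputed for unsampled patients. The cost is some extra modelling. Clearance will be imprecise from one sample, particularly for DFX, because Section 11.8 pools only DFP data from DEEP-1.

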3. BACKGROUND

3.1Condition

Haemoglobinopathies are a group of inherited disorders characterized by structural variations of the haemoglobin molecule which often lead to ineffective erythropoiesis. Frequent blood transfusions are the recommended treatment to suppress ineffective erythropoiesis and to provide adequate oxygen carrying capacity. Patients become iron overloaded within 3 to 24 months of a transfusion regimen aimed to maintain a minimum haemoglobin (Hb) concentration of 9.5 to 10.5 g/dL.

Examples of transfusion-dependent anaemias include aplastic anaemia, Diamond-Blackfan anaemia (red blood cell aplasia), dyserythropoietic anaemias, Fanconi anemia (hypoplastic anaemia), myelodysplastic syndromes, sickle cell disease (SCD) and thalassaemia major. Some of these anaemias are genetic, start

early in the life and affect children as well as adults. Hereditary haemoglobinopathies such as thalassemia major and SCD are the most representative in this group.

This study will include **hereditary haemoglobinopathies requiring chronic transfusion therapy, including but not limited to thalassemia syndromes and sickle cell disease (SCD)**.

Unfortunately, all chronically transfused patients become clinically iron overloaded as there is no physiological mechanism for the removal of the excess of transfused iron from the body.

The pathologic changes and clinical manifestations associated to chronic iron overload are common among all chronically transfused patients, albeit best documented in patients with thalassemia major. In the most severe forms of transfusion-dependent anaemia, after only few years on regular transfusion regimen, the iron storage capacity of the liver and other organs (heart and endocrine organs) is exceeded, thus leading, in the absence of adequate intervention, to the development of a multi-system organ dysfunction. For example in thalassemic patients, it has been demonstrated that, after the age of 8-10 years, patients are at risk of developing severe complications related to iron accumulation, i.e. growth retardation, with 25% to 60% of patients being reported below the third percentile of height (Gabutti V and Piga A, 1996; Cappellini MD et al., 2008). Arrested puberty, reported in 38-80% of males and 30-70% of females, is also a relatively common complication in moderately or grossly iron overloaded patients with thalassaemia, and is characterised by a lack of pubertal progression over a year or more leading to failure or delay of sexual maturation (Gabutti V and Piga A, 1996).

Iron overload may be prevented or treated with chelating agents capable of complexing with iron and promoting its excretion. The introduction of chelation therapy combined with the regular transfusions since the early 1980s, has changed radically the clinical history of thalassaemia and other hereditary haemoglobinopathies, leading to a significant survival increase and to a relevant improvement in the patients QoL (Borgna-Pignatti C et al., 2006; Ceci A et al., 2006).

In the current clinical practice iron chelating treatment in thalassaemia major patients starts when serum ferritin levels reach about 1000 µg/L, which usually occurs after 10-20 blood transfusions when the patient can be on average 2 or 3 year old or less depending from the amount of transfused red blood cells.

The first chelating agent approved for clinical use was deferoxamine (DFO) which has played a central role in the iron overload treatment.

Deferoxamine treatment has satisfactory therapeutic effects, but the prognosis remains poor because its requirement for prolonged subcutaneous infusion make the drug too burdensome for full adherence, thus leading to poor or non-compliance in a high percentage of patients, particularly in the paediatric population (Giardina PJ et al., 2001). Moreover, 10-15% of subjects are unable to use this chelator due to hypersensitivity or toxic side effects.

Starting from these considerations, in the recent years many oral compounds have been studied. Research has led to the identification of several interesting molecules but, among these, only two agents became available on the European Market: deferiprone and deferasirox.

Deferiprone (DFP, Ferriprox®) is the first oral iron chelating agent introduced in Europe. It was authorised by the European Medicines Agency (EMA) in 1999 for the treatment of patients with thalassaemia major when DFO therapy is contraindicated or inadequate. Initially, the MA was granted on the basis of evidence collected in small clinical studies. However, later controversies regarding DFP safety and efficacy prompted the appropriate investigation of its use in large post-marketing surveillance programs where data from over 6000 patients using DFP in some case for more than 10 years, have been collected (Ceci A et al., 2002; al-Rafaie FN et al., 1994; Taher A et al., 2001; Olivieri NF et al., 1997; Ceci A et al, 2011). Recently the EMA has

updated the Summary of Product Characteristics (SmPC) including the statement that "DFP demonstrated to be superior to DFO in decreasing cardiac iron load" (Ferriprox® SmPC 2010).

However, despite wide experience of DFP in patients with iron overload (specifically thalassaemic) limited data are available for younger children. Thus, due to a lack of data submitted to the Regulatory agency from comparative studies, the drug is still approved only for second line treatment. Consequently, the need for additional data on DFP was expressly included by the PDCO (the Paediatric Committee at the EMA) in the 2009 PDCO Priority List and an independent research Consortium (DEEP- Deferiprone Evaluation in Paediatrics) has been set up and funded by the European Commission under the FP7 Framework Research program "HEALTH-2010.4.2-1: Off-patent medicines for children".

Deferasirox (DFX, Exjade®) the second approved oral chelator, is a once-daily orally active iron chelator, firstly introduced in USA, and authorised in Europe under the Centralised Procedure for treating chronic iron overload due to frequent blood transfusions (≥ 7 ml/kg/month of packed red blood cells) in patients with beta thalassaemia major above 6 years of age and in patients under 6 years of age when DFO therapy is contraindicated. The safety and efficacy profile of DFX was compared with DFO, and non-inferiority to this drug was demonstrated in patients with LIC ≥ 7 mg Fe/g dw. Post marketing long-term data have identified renal impairment as a safety risk associated with DFX therapy in both paediatric and adult patients and consequently the SmPC has been updated accordingly (Annex 1). Nevertheless, DFX with its PK profile allowing the maintenance of plasma levels within the therapeutic range for 24-hour period, and permitting once-daily oral administration, is currently the most widely used chelator in the paediatric subset (Ceci A et al., 2011).

